We propose a double-blinded, randomized parallel group study that will randomize older adults with musculoskeletal pain and poor sleep quality to oral self-administration of either GABA (two 250mg capsules for a total of 500mg daily) or Placebo during four weeks. Our study design was guided by recommendations by the IMMPACT group for clinical pain trials [23][24][25][26] see table 1. After initial screening, eligible participants will undergo two 2.5-hour baseline sessions (health, sensory, and neuroimaging) for the collection of clinical information, QST, and brain imaging data. During the entire study, participants will wear a OURA ring to objectively measure sleep quality. During the intervention, participants will receive a phone call once a week for an assessment of adverse effects and compliance. During the last week of the intervention period, two assessment sessions will follow, these will be identical to the baseline sessions. (Figure 5.)

To reduce participant burden and exposure risk to COVID-19, the ICF may be conducted remotely via phone calls, UF Zoom and/or online (REDCap). A copy of the signed ICF will be provided to the participant.

Participants: Older adults over 45 years of age who have a smartphone and have experienced pain of at least moderate intensity (>5/10 pain intensity ratings) on more days than not during the past three months, and who also reported poor sleep quality (>5 PSQI scores) will be considered for participation. Community-based recruitment methods established in [name] lab will be utilized.

Exclusion criteria will align with study and safety requirements broadly related to GABA administration, pain and MRI : 1) serious psychiatric conditions (e.g., schizophrenia, major depression, bipolar disorder;

Table 1. Study measures consistent with core outcome domains recommended by IMMPACT- www.immpact.org

IMMPACT Core Outcome Domain	Proposed Study Measures
Pain	Verbal Descriptor Scale (VDS) WOMAC-Pain
Physical functioning	WOMAC-Physical Function
Socio-emotional functioning	BDI-II PANAS
Sleep	Pittsburgh Sleep Quality Index Berlin Questionnaire Epworth Sleepiness Scale OurA Ring Sleep Diary
Improvement and satisfaction with treatment	Multidimensional Patient Impression of Change

Symptoms and adverse events	Passive capture of spontaneously reported adverse events and symptoms, with the use of open-ended prompts

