Assessment of Adverse Events. A standard operating procedure will be established which is followed to collect and deal with adverse events during the research project. In particular, adverse events will be systematically monitored both during the treatment phases, as well as 3 months following study completion. In particular, participants will respond to a side effect checklist to detect any possible physiological reactions related to the drug administration. This will include a series of open-ended questions asked by trained research staff regarding any adverse events that have occurred since the last visit or phone contact. Additionally, during the 3 months follow up, participants will be asked to the WOMAC PANAS and PSQI questionnaires to assess pain, feelings, and sleep respectively. This report will be reviewed by the principal investigator and study physician in a timely fashion. Any serious untoward event, whether related or unrelated to the study drug or procedures, will be reported to the UF IRB.

Adverse events will be defined as any physical symptoms or side effects that began following the administration of the study drug. All reported and observed adverse events will be tracked in a running adverse events participant log, which will contain information regarding dates, description, and severity. All adverse events will be coded using the most current version of the Medical Dictionary for Regulatory Activities (MedDRA). The number and percentage of participants reporting treatment-

emergent adverse events will be tabulated by treatment, system organ class, and MedDRA-preferred term. Treatment-emergent adverse events will be those adverse events that begin or worsened following the first dose of study drug. Adverse events will be further classified by severity and investigator-assigned relationship to study drug. All reported and observed adverse events will be tracked on a running adverse events log (specific to each subject and maintained in his/her study file) and will contain information regarding onset/offset dates, time course (i.e., single, sporadic), severity, action taken regarding study drug, relationship to study drug, and whether it meets FDA criteria for "Serious." Each reported event is reviewed by the principal investigator and the study physician in a timely fashion. Additionally, the principal investigator reviews all adverse events recorded in each participant's log after study participation.

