Data and Safety Monitoring Plan. A Data Safety Monitoring Plan will be in place. In particular, the following procedures will be implemented to ensure data and participant safety. Study progress and safety will be reviewed by the principal investigators in collaboration with a physician, and the study MD. We will stop the intervention if 30% or more of the participants in the GABA condition report seven or more (out of forty-four) of the side effects at moderate to severe levels over more than 3 days as acquired during the weekly check-in phone calls during the intervention phase. Data collected before the stop of intervention will be used for analysis. All participants who went through the intervention phase of the study will be followed up by phone calls for 7 days to ensure safety. Progress reports, including participant recruitment, retention/attrition, and adverse events will be provided to an Independent Safety Monitor for reviews on a bi-annual basis. The Independent Safety Monitor for this study will consist of an established senior investigator not associated with our study. A study end report will be compiled and will include a list and summary of adverse events. Also, this report will address: (1) whether adverse event rates are consistent with pre-study assumptions; (2) reason for dropouts from the study; (3) whether all participants met entry criteria; (4) whether continuation of the study is justified on the basis that additional data are needed to accomplish the stated aims of the study; and (5) conditions whereby the study might be terminated prematurely. The annual report will be signed by the Independent Safety Monitor and will be forwarded to the IRB, NIH, and FDA. The Data Safety Monitoring Plan will also require that all significant serious adverse events that may be possibly related to the study participants will be reported to the IRB, FDA, and NIH within 48 hours of the principal investigator's learning of the event. Besides, any unanticipated serious adverse events that may increase the risk of the research for participants or potential participants will be reported to the IRB and the NIH within 48 hours of the principal investigators being informed about the event. This study will be stopped before its completion if: (1) the intervention is associated with adverse effects that significantly impact the risk-benefit ratio, (2) study recruitment or retention becomes futile, (3) any new information becomes available during the trial that necessitates stopping the trial; or (4) if independent safety monitor indicates stopping trial is necessary due to adverse event frequency or severity.

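### The Independent Safety Monitor may call for stopping on adverse events, but is left off both 48-hour serious event reports and is scheduled to see adverse event data only bi-annually

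*Combined protocol and SAP*

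**What the plan says.** All but two of the relevant statements are in section 6, Data and Safety Monitoring Plan.

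- **Authority.** The fourth condition for ending the study early applies "if independent safety monitor indicates stopping trial is necessary due to adverse event frequency or severity". No numerical threshold is attached. The monitor is described as a senior investigator from outside the study.
- **Routine information.** "Progress reports, including participant recruitment, retention/attrition, and adverse events will be provided to an Independent Safety Monitor for reviews on a bi-annual basis".
- **Expedited information, possibly related serious events.** These "will be reported to the IRB, FDA, and NIH within 48 hours of the principal investigator's learning of the event".
- **Expedited information, unanticipated serious events that may raise risk.** These "will be reported to the IRB and the NIH within 48 hours of the principal investigators being informed about the event".
- **Serious events in general** (section 6, Assessment of Adverse Events). "Any serious untoward event, whether related or unrelated to the study drug or procedures, will be reported to the UF IRB".
- **Reports that weigh the evidence.** A report at study end is to address, among other items, "whether continuation of the study is justified on the basis that additional data are needed". The plan then says that an annual report is signed by the monitor and forwarded to the IRB, NIH and FDA.

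Section 5, Second Phase of the Study, sets the exposure: "oral self-administration of either GABA (two 250mg capsules for a total of 500mg daily) or Placebo during four weeks".

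**The concern.** The plan treats 48 hours as the right speed for serious events, yet leaves out the one role that it empowers to stop the trial on their severity. A team that follows the text exactly would tell the IRB and NIH (and the FDA, for possibly related events) within two days. It would tell the monitor at the next bi-annual report. Nothing in the documents gives the monitor a faster or event-triggered route.

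At stake is whether the fourth stopping condition can work while it still matters. Treatment is short and the sample is small, so a delay of months can span several full courses and a sizeable share of enrolment.

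The reporting cycle is also unclear. The plan uses three labels (bi-annual progress report, study end report, annual report) without saying how they relate. The items most useful to someone deciding whether to continue sit under the study end report, when no such decision remains.

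**Working it through.** The plan gives no figure to reproduce here. The check compares recipients and then does the timing arithmetic.

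**1. Who receives what, and when**

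| Information | Timing | Recipients named | Monitor named? |
|---|---|---|---|
| Serious, possibly related | 48 hours | IRB, FDA, NIH | No |
| Serious, unanticipated, may raise risk | 48 hours | IRB, NIH | No |
| Any serious untoward event | Not stated | UF IRB | No |
| Progress report with adverse events | Bi-annual | Monitor | Yes |
| Annual report | Annual | Signed by monitor, then IRB, NIH, FDA | Yes |

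The fastest scheduled route to the monitor is the bi-annual report.

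**2. Inputs**

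- Reporting interval: bi-annual, read as six-monthly, 52/2 = 26 weeks or 26 × 7 = 182 days (a reading, because the plan does not state months).
- Treatment length: 4 weeks (section 5, Second Phase and Intervention Period).
- Sample: 28, with 14 per arm (Power and sample size considerations).
- Accrual time: not in the documents. Assumed range 6 to 36 months, with even accrual.

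**3. Delay against treatment length**

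- Courses per interval: 26/4 = 6.5.
- Longest wait for an event to reach the monitor: 26 weeks. Average wait, if events fall evenly over the interval: 26/2 = 13 weeks.
- Chance that a scheduled report falls within a given participant's course: 4/26 = 0.154, about 15%.

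**4. Participants starting capsules in one interval**

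Formula: starts = min(28, 28 × 26 / accrual weeks), where accrual weeks = months × 52/12. With equal allocation, half of these are on GABA.

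| Assumed accrual | Weeks | Starts per 26 weeks | Of which GABA |
|---|---|---|---|
| 6 months | 26 | 28 | 14 |
| 12 months | 52 | 14 | 7 |
| 18 months | 78 | 9.3 | 4.7 |
| 24 months | 104 | 7 | 3.5 |
| 36 months | 156 | 4.7 | 2.3 |

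These are worst cases, for an event just after a report. Over the average wait of 13 weeks the counts halve where accrual is even: 28 × 13/52 = 7 at 12 months and 28 × 13/104 = 3.5 at 24 months.

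**5. Effect of the fix**

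Copying the monitor on the two existing 48-hour reports cuts the longest scheduled wait for those events from 182 days to 2. Non-serious event data would still arrive at the bi-annual interval.

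**The case against.** The strongest reply is that the trial has timely safety review that does not run through the monitor, and this stands.

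- Participants are called weekly. Moderate or severe symptoms go to the principal investigator, with the study physician consulted as needed, and participants can be discontinued for adverse events (Intervention Period).
- The principal investigator and study physician review each event (Assessment of Adverse Events).
- A separate rule stops the intervention once 30% of the GABA arm crosses a side-effect threshold. At full enrolment that means at least 5 of 14, because 0.30 × 14 = 4.2.
- The risk-benefit and new-information stopping conditions do not need the monitor.
- The IRB, NIH and FDA are outside bodies and hear of serious events within 48 hours as listed.

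These routes do not fully replace the monitor. The 30% rule counts participants with many side effects, so one serious event would not trigger it. It also needs counts by arm in a double-blind trial that names no unblinded reviewer. The investigators belong to the study team. The outside bodies are informed, but the plan gives the frequency-or-severity call to the monitor.

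A second reply is that nothing forbids an ad hoc call to the monitor, and that the adverse event operating procedure, still to be established, might require one. That is fair. But the plan does list recipients, and the monitor is not among them.

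Four stronger readings are tempting and not supported:

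- *The monitor cannot act in time.* This depends on accrual, which is not given. At 12 months or longer, one interval covers half the sample or less, so a report early in accrual could still protect people not yet started.
- *A cluster of non-serious events could sit with the IRB and NIH for months while the monitor is unaware.* Only serious events go to those bodies promptly.
- *Continuation is considered only at study end.* The annual report that the monitor signs points to inconsistent labels rather than to that design.
- *Bi-annual means every two years.* This fits poorly with an annual report signed by the same person.

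**Conclusion.** The point holds as a gap between the monitor's authority and the monitor's information. The monitor can call for a stop on adverse event severity, but is absent from both 48-hour lists and is scheduled to see adverse events only bi-annually. On a six-monthly reading, a serious event may take up to about 26 weeks to arrive. That may be too late to act, and it will usually fall outside the affected participant's own four-week course.

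The number of later participants exposed in the meantime rests on an assumed accrual time. It is 7 to 14 of 28 across both arms for 24 to 12 months, and about 5 to 28 over the wider range of 36 to 6 months. The recipient lists can be read directly from the text and need no assumption.

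A reader should not conclude that the trial lacks timely safety review or that independent oversight fails altogether. This is a specific, inexpensive improvement to the monitoring plan.

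**What to change.** In the Data and Safety Monitoring Plan:

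1. Add the Independent Safety Monitor as a recipient in both 48-hour serious event sentences.
2. State the monitor's review interval in months.
3. Reconcile the bi-annual, annual and study end reports. Place items (1), (4) and (5) of the end report (event rates against prior expectation, continuation, grounds for early termination) in the periodic report that the monitor reviews while the trial is running.

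The cost is protocol wording and a copy of reports already being written for the IRB and NIH. The downside is a few unscheduled reads for the monitor. No visit, procedure, dose or clinical rule changes.

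Extra summaries to the monitor after particular non-serious events or discontinuations would be new documents. They are optional and are not needed to close this gap.
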